4.3.1.2. Within groups assessment

For each group, at each time point that blood samples are collected for humoral immune response and for each assay (unless otherwise specified):

- Percentage of participants above pre-defined assay cut-off and their exact 95% CI will be tabulated.
- Percentage of participants above seroprotection/seroconversion rate for HI antibody titer and their exact 95% CI will be tabulated.
- ~~CCI~~ /GMTs and their 95% CI will be tabulated.
- MGI will be tabulated with 95% CI.
- Antibody titer/concentration will be displayed using reverse cumulative curves.

The above mentioned descriptive within group immunogenicity analysis will also be generated by age at first vaccination (65-69 YOA, 70-79 YOA, ≥ 70 YOA and ≥ 80 YOA years).

- Additionally, the CBER and CHMP criteria for HI SPR and SCR will be assessed as follows:

CBER criteria to be evaluated:

- The lower limit (LL) of the 95% CI for SCR should be $\geq 30\%$ in participants ≥ 65 YOA.
- The LL of the 95% CI for SPR should be $\geq 60\%$ in participants ≥ 65 YOA.

CHMP criteria to be evaluated:

- At least one of the 3 following criteria should be met:
- the point estimates of SPR $> 60\%$, SCR $> 30\%$, and MGI > 2.0 for elderly > 60 years for each of the antigen strains.

These above defined analyses evaluating the CBER and CHMP criteria should be interpreted with caution considering that there is no adjustment for multiplicity for these comparisons.

4.3.2. Safety analysis

The safety analysis will be performed on the ES as follows:

- The number and percentage of participants and doses with at least one administration site event AE (solicited and unsolicited), with at least one systemic AE (solicited and unsolicited) and with any AE during the 4-day (i.e. the day of vaccination and 3 subsequent days) and 30-day (i.e. the day of vaccination and 29 subsequent days) follow-up period will be tabulated with exact 95% confidence interval (CI) after each dose and overall. The same computations will be done for Grade 3 AEs, for Grade 3 non-serious AEs and for AEs resulting in a medically attended visit.

These analyses will present all solicited and unsolicited AEs, including SAEs and pIMDs (unless otherwise specified).

The above analysis will also be performed for the solicited symptoms only during the 4-day (i.e. the day of vaccination and 3 subsequent days) follow-up period.

- The number and percentage of participants reporting each individual solicited administration site AE (any grade, Grade 3 and resulting in medically attended visit) and solicited systemic AE (any grade, Grade 3 and resulting in medically attended visit) during the 4-day follow-up period (i.e. the day of vaccination and 3 subsequent days) will be tabulated for each group after each dose and overall. The percentage of doses followed by each individual solicited administration site AE (any grade, Grade 3 and resulting in medically attended visit) and solicited systemic AE (any grade, Grade 3 and resulting in medically attended visit) during the 4-day follow-up period (i.e. the day of vaccination and 3 subsequent days) will be tabulated, with exact 95% CI.
- For fever, the number and percentage of participants reporting fever by half degree (°C) cumulative increments during the 4-day follow-up period (i.e. the day of vaccination and 3 subsequent days) will be tabulated for each group after each dose and overall.
- The percentage of participants with each solicited administration site event and solicited systemic event (any grade and Grade 3) will be represented graphically for each group after each dose.
- The number of days with solicited events reported during the 4-day follow-up period will be tabulated for each individual solicited event using descriptive statistics (mean, minimum, Q1, median, Q3, maximum). The same computations will be done for Grade 3 solicited events.
- The number of days with solicited events ongoing beyond the 4-day follow-up period will be tabulated for each individual solicited event using descriptive statistics (mean, minimum, Q1, median, Q3, maximum). The same computations will be done for Grade 3 solicited events.

- The number and percentage of participants with any unsolicited AEs during the 30-day follow-up period (i.e. the day of vaccination and 29 subsequent days) with its exact 95% CI will be tabulated by group and by Medical Dictionary for Regulatory Activities (MedDRA) System Organ Class (SOC), High Level Term (HLT) and Preferred Term (PT). Similar tabulation will be done for Grade 3 unsolicited AEs, for any causally related unsolicited AEs, for Grade 3 causally related unsolicited AEs and for unsolicited AEs resulting in a medically attended visit. The verbatim reports of unsolicited AEs will be reviewed by a physician and the signs and symptoms will be coded according to the MedDRA Dictionary for Adverse Reaction Terminology. Every verbatim term will be matched with the appropriate Preferred Term. The above analysis by dose will also be performed.
- The number and percentage of participants with at least one report of SAE classified by the MedDRA Primary SOC, HLT and PTs and reported after vaccine administration (Day 1) up to study end (6 months after last vaccination) will be tabulated with exact 95% CI.
- The number and percentage of participants with at least one report of causally related SAE classified by the MedDRA Primary SOC, HLT and PTs and reported after vaccine administration (Day 1) up to study end (6 months after last vaccination) will be tabulated with exact 95% CI.
- The same tabulation will be presented for fatal SAEs.
- All SAEs will also be described in detail in a tabular listing.
- All pIMD will also be described in detail in a tabular listing.
- All AEs/SAEs leading to study/intervention discontinuation from dose 1 up to study end will be tabulated.
- The percentage of participants with at least one report of pIMD classified by the MedDRA SOC, HLT and Preferred Terms and reported after vaccine administration (Day 1) up to study end (6 months after last vaccination) will be tabulated with exact 95% CI.
- The percentage of participants with at least one report of related pIMD classified by the MedDRA SOC, HLT and Preferred Terms and reported after vaccine administration (Day 1) up to study end (6 months after last vaccination) will be tabulated with exact 95% CI.
- The number and percentage of participants using concomitant medication (any medication and any antipyretic) during the 4-day and the 30-day follow-up period after each dose and overall will be tabulated with exact 95% CI.
- The number and percentage of participants using concomitant vaccination during the 30-day follow-up period after each dose and overall will be tabulated with exact 95% CI.
- Compliance in completing solicited events information will be tabulated after each dose and overall.

Some of the key safety analysis will be generated by age group at first vaccination (65-69 YOA, 70-79 YOA, \geq 70 YOA and \geq 80 YOA years) as mentioned below.

[figure not shown]
- The number and percentage of participants reporting each individual solicited administration site AE (any grade, Grade 3 and resulting in medically attended visit) and solicited systemic AE (any grade, Grade 3 and resulting in medically attended visit) during the 4-day follow-up period (i.e. the day of vaccination and 3 subsequent days) will be tabulated for each group after each dose and overall.

The number and percentage of participants with any unsolicited AEs during the 30-day follow-up period (i.e. the day of vaccination and 29 subsequent days) with its exact 95% CI will be tabulated by group and by MedDRA Primary SOC, HLT and PTs

- For clinicaltrials.gov and EudraCT posting purposes, percentage of participants of combined solicited and unsolicited non-serious adverse events during the 30-day follow-up period (i.e. the day of vaccination and 29 subsequent days) will be produced by System Organ Class and preferred terms and according to occurrence of each event.

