1.2. Study Design

The current study is designed to assess the immunogenicity, safety and reactogenicity of the RSVPreF3 OA investigational vaccine when co-administered with a FLU vaccine, compared with administration of the vaccines separately. There are 2 parallel arms:

- **Co-Ad group:** Participants will receive a single dose of RSVPreF3 OA investigational vaccine and a single dose of FLU vaccine at Visit 1 (Day 1).
- **Control group:** Participants will receive a single dose of FLU vaccine at Visit 1 (Day 1), followed by a single dose of the RSVPreF3 OA investigational vaccine at Visit 2 (Day 31).

All participants will be followed up for safety (in terms of SAEs and pIMDs) for 6 months after the last study vaccine administration.

Figure 1 Study design overview

1MPD = 1-month post-dose.

* Blood sample only from participants in Control group.

FLU = FLU HD quadrivalent; RSV = RSVPreF3 OA investigational vaccine; BS = Blood sample from all participants (except for blood sample at Visit 3 which is only applicable for Control group).

Note: Unsolicited AEs will be collected from first dose to 30 days post-dose. SAEs and pIMDs will be collected from first dose through the entire study period. SAEs related to study participation will be collected from the time of consent.

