4. STATISTICAL ANALYSES

4.1. General Considerations

4.1.1. General Methodology

95% CI for proportion will be based on exact Clopper-Pearson confidence interval [[Clopper](#), 1934].

95% CI for group difference in proportion will be based on Miettinen and Nurminen confidence interval [[Miettinen](#), 1985].

The group adjusted GMT ratio will be based on a back transformation of group contrast in an ANCOVA model applied to the logarithm- transformed titers.

Primary Analysis: The ANCOVA model will include the treatment group and age category (age at vaccination: 65-69, 70-79 or ≥ 80 years) as fixed effects and the pre-dose log-10 titer as regressors.

Sensitivity Analysis: The ANCOVA model will include the treatment group and age category (age at vaccination: 65-69, 70-79 or ≥ 80 years) as fixed effects, center as the random effect and the pre-dose log-10 titer as regressors.

95% CI for GMT will be based on a back transformation of student CI for the mean of log-transformation.

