5. SAMPLE SIZE DETERMINATION

The target enrolment will be 1028 participants (514 in the group receiving the RSVPreF3 OA investigational vaccine co-administered with the FLU vaccine (Co-Ad group) and 514 in the Control group where RSVPreF3 OA investigational vaccine and FLU vaccine are administered staggered) to obtain at least 924 evaluable participants (462 in the Co-Ad group and 462 in Control group) for the evaluation of the primary objectives, assuming that approximately 10% of the enrolled participants will not be evaluable.

Each objective will be evaluated with a nominal type I error of 2.5%.

Table 2 Overall power to demonstrate primary objectives: non-inferiority of the immunogenicity of RSVPreF3 OA investigational vaccine when co-administered with FLU vaccine as compared to when administered alone- assuming 462 participants are available in each group

Endpoint	Standard deviation of log ₁₀ concentration	Reference ratio	Non-inferiority margin	Type II error	Power
RSV-A Non-inferiority* (1-sided test with alpha = 2.5%)					
GMTs RSV-A neutralization antibody	0.45	1.05	1.5	0.1%	99.9%
FLU Non-inferiority* (1-sided test with alpha=2.5%)					
GMTs HI H1N1 strain	0.6	1.05	1.5	2.5%	97.5%
GMTs HI H3N2 strain	0.6	1.05	1.5	2.5%	97.5%
GMTs HI B/Yamagata	0.6	1.05	1.5	2.5%	97.5%
GMTs HI B/Victoria strain	0.6	1.05	1.5	2.5%	97.5%
RSV-B Non-inferiority* (1-sided test with alpha = 2.5%)					
GMTs RSV-B neutralization antibody	0.45	1.05	1.5	0.1%	99.9%
Global Type II error to show non-inferiority					~10.0%
Global power					~90.0%

* Pass 2019 alpha = 2.5%, Two-Sample T-Tests for Non-Inferiority Assuming Equal Variance and Equal mean

For RSV: non-inferiority limit = 0.176 (=log₁₀[1.5]).

For each Flu vaccine strain: non-inferiority limit = 0.176 (=log₁₀[1.5]).

Reference Ratio= 0.0212 (=log₁₀[1.05])

Considering a slight interference of 1.05 in true GMTs in both groups with a common population standard error of 0.45 for the RSV-A and RSV-B neutralization antibodies and 0.6 for each of the FLU strains in log₁₀ transformed concentration, the study has at least 90.0% power to meet the primary objectives.

Nominal powers to evaluate secondary objective

The nominal power to evaluate the non-inferiority on seroconversion rate for each of the FLU strains is above 86%, depending on the plausible rates.

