6.1.5. Concomitant Medications

The number and percentage of participants and doses using concomitant medication (any medication, any antipyretic and any antipyretic taken prophylactically, respectively) during the 4-day follow-up period (i.e., on the day of vaccination and 3 subsequent days) and during the 30-day follow-up period (i.e., on the day of vaccination and 29 subsequent days) will be summarized by group after each vaccine dose and overall.

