6.2.3.9. Counting rules for occurrences of solicited events

When the occurrences of solicited events are summarized, each event recorded as having occurred during a specific period will be counted as only one occurrence regardless of the number of days on which it occurs. Also, in the case of co-administered study interventions, an administration site event recorded for a participant following multiple study interventions will be counted as only one occurrence.

Table 4 Intensity grading scale for solicited events

Event	Intensity Grade	Parameter
Pain at administration site	0	None
	1	Mild: Any pain neither interfering with nor preventing normal everyday activities.
	2	Moderate: Painful when limb is moved and interferes with everyday activities.
	3	Severe: Significant pain at rest. Prevents normal everyday activities.
Erythema at administration site		Greatest surface diameter in mm
Swelling at administration site		Greatest surface diameter in mm
Temperature*		Temperature in °C.
Headache	0	None
	1	Mild: Headache that is easily tolerated
	2	Moderate: Headache that interferes with normal activity
	3	Severe: Headache that prevents normal activity
Fatigue	0	None
	1	Mild: Fatigue that is easily tolerated
	2	Moderate: Fatigue that interferes with normal activity
	3	Severe: Fatigue that prevents normal activity
Myalgia	0	None
	1	Mild: Myalgia that is easily tolerated
	2	Moderate: Myalgia that interferes with normal activity
	3	Severe: Myalgia that prevents normal activity
Arthralgia	0	None
	1	Mild: Arthralgia that is easily tolerated
	2	Moderate: Arthralgia that interferes with normal activity
	3	Severe: Arthralgia that prevents normal activity

The route for measuring temperature can be oral or axillary. Fever is defined as temperature $\geq 38.0^{\circ}\text{C}$ regardless of the location of measurement.

The maximum intensity of local injection site erythema/swelling and fever will be scored at GSK as follows:

	Erythema/swelling	Fever
0:	$\leq 20\text{mm}$	$< 38.0^{\circ}\text{C}$
1:	$> 20 - \leq 50\text{mm}$	$\geq 38.0^{\circ}\text{C} - \leq 38.5^{\circ}\text{C}$
2:	$> 50 - \leq 100\text{mm}$	$> 38.5^{\circ}\text{C} - \leq 39.0^{\circ}\text{C}$
3:	$> 100\text{mm}$	$> 39.0^{\circ}\text{C}$

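### Pooled Control dose percentages get exact binomial intervals that ignore two doses per participant, so those intervals may be slightly too narrow

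*SAP*

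**What the plan says.** The first bullet of SAP 4.3.2 covers two units of analysis: "The number and percentage of participants and doses with at least one administration site event AE (solicited and unsolicited", and likewise for systemic and any adverse events. Results for the 4-day and 30-day "follow-up period will be tabulated with exact 95% confidence interval (CI) after each dose and overall". The same computations are repeated for Grade 3, Grade 3 non-serious and medically attended events, and for solicited symptoms alone over 4 days. The second bullet adds "The percentage of doses followed by each individual solicited administration site AE (any grade, Grade 3 and resulting in medically attended visit", and the same for systemic events, again with exact 95% intervals.

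The method is fixed in SAP 4.1.1: "95% CI for proportion will be based on exact Clopper-Pearson confidence interval". No other method is named for a single proportion.

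Control participants receive FLU at Day 1, "followed by a single dose of the RSVPreF3 OA investigational vaccine at Visit 2 (Day 31" under SAP 1.2. SAP 5 plans "514 in the Control group where RSVPreF3 OA investigational vaccine and FLU vaccine are administered staggered". SAP 6.2.1 attributes each event to the most recent dose, so a fully vaccinated Control participant supplies two dose records. Neither document has a clustering adjustment or a caveat for dose-level rows.

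**The concern.** Clopper-Pearson inverts the binomial distribution and so needs independent records. In the overall Control dose row the records come in pairs from the same person, reported on the same kind of diary. A person who reports fatigue after one vaccine may well be more likely to report it after the other. Positive correlation raises the variance of the pooled percentage above the binomial value, and an interval labelled exact 95% can then cover less than 95% of the time.

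The affected rows are limited:

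- Rows for a single dose hold one record per person and are valid.
- Participant-level rows, including the overall ones, are also valid.
- The Co-Ad group has one vaccination visit. SAP 6.2.3.9 says that with co-administration "an administration site event recorded for a participant following multiple study interventions will be counted as only one occurrence". The point is therefore raised for Control only.

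What is at stake is the stated precision of supplementary descriptive rows. The safety endpoints in SAP 1.1 are percentages of participants, and no safety hypothesis is tested.

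**Working it through.** The plan states no width or coverage for its safety intervals, so there is no figure of its own to reproduce.

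**Inputs from the documents.** 514 Control participants (SAP 5); two doses each (SAP 1.2), so 2 × 514 = 1028 doses; two-sided 95% Clopper-Pearson (SAP 4.1.1).

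**Assumed inputs.** Event rates p1 (after FLU) and p2 (after RSV), and the within-person correlation rho between the two outcomes. The documents give none of these, so a range is shown.

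**Standard error.** Write q = 1 − p, and pbar for the mean of p1 and p2. Then

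true SE / binomial SE = sqrt( [p1q1 + p2q2 + 2·rho·sqrt(p1q1p2q2)] / (2·pbar·qbar) ).

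- Equal rates: the ratio is sqrt(1 + rho), for example sqrt(1.3) = 1.14 at rho 0.3.
- 30% and 50%: (0.21 + 0.25 + 0.458·rho) / 0.48, which equals 1 at rho = 0.02 / 0.458 = 0.04.
- 20% and 60%: (0.16 + 0.24 + 0.392·rho) / 0.48, which equals 1 at rho = 0.08 / 0.392 = 0.20.

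Unequal rates thus offset the clustering, because the pooled binomial variance overstates the variance within each dose.

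**Coverage.** Each participant contributes 0, 1 or 2 doses with the event. Convolving that distribution 514 times gives the exact distribution of the event total. Coverage is the probability that the interval on 1028 doses contains pbar.

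| Rates (FLU/RSV) | rho 0 | 0.1 | 0.2 | 0.3 | 0.4 | 0.5 |
|---|---|---|---|---|---|---|
| 30% / 30% | 95.2% | 94.0% | 92.8% | 91.7% | 90.5% | 89.3% |
| 30% / 50% | 95.6% | 94.5% | 93.4% | 92.3% | 91.2% | 90.0% |
| 20% / 60% | 96.9% | 96.1% | 95.2% | 94.3% | 93.3% | not possible |
| 1% / 1% | 95.8% | 94.8% | 93.7% | 92.6% | 91.4% | 90.3% |
| 2% / 2% | 96.7% | 95.8% | 94.8% | 93.8% | 92.8% | 91.8% |
| 0.5% / 0.5% | 97.8% | 97.1% | 96.4% | 95.7% | 94.8% | 93.9% |

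At 20% and 60%, rho cannot exceed (0.20 − 0.12) / 0.196 = 0.41.

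**Effect on the limits.** Take an observed 30% and equal rates, so that the design effect is 1 + rho and the effective n is 1028 / (1 + rho).

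| rho | Effective n | 95% interval |
|---|---|---|
| as planned | 1028 | 27.2% to 32.9% |
| 0.2 | 856.7 | 26.9% to 33.2% |
| 0.3 | 790.8 | 26.8% to 33.3% |
| 0.5 | 685.3 | 26.6% to 33.6% |

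Each limit moves by 0.3 to 0.7 percentage points.

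**The case against.** The strongest objection is that this may not matter in practice. Valid intervals for Control after FLU, after RSV and per participant overall appear in the same set of tables, so only a supplementary row is in question. The harm also depends on quantities the documents do not give. The two Control doses are different products, so equal rates are not the natural default. With rates of 10% and 40%, for example, coverage is 96.5%, 95.7% and 94.8% at rho 0, 0.1 and 0.2. Even at rho 0.5 the limits move by less than one percentage point.

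All of that stands, and it is why the point is minor and conditional. It does not make the rule correct. The plan assumes independence without support, and coverage falls below nominal at modest correlation when the two rates are similar or moderately different.

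Two textual limits also stand. Only the first bullet of SAP 4.3.2 expressly joins doses, an overall row and an exact interval. The sentence on doses followed by each solicited event does not say overall, so pooling there is an inference. And SAP 6.1.5 and 6.1.6, which offer a model for dose rows without an interval, are silent on intervals rather than ruling them out.

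**Conclusion.** The concern holds, as a minor point. Under the rule as written, the overall Control dose rows treat up to 1028 paired records as independent, and nothing in either document corrects for it. For rho between 0.1 and 0.3, coverage is 94.0% to 91.7% at equal rates of 30%, and 96.1% to 94.3% at 20% and 60%. The shortfall is small or absent when the two vaccines' rates differ widely, rho is low, or events are very rare (about 0.5%). These results rest on assumed rates and correlations and on 514 participants who all receive both doses. No endpoint, point estimate or non-inferiority conclusion changes.

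**What to change.** Add one sentence to SAP 4.3.2 for dose rows that pool both Control doses, choosing one of two options.

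- **(a) Omit the interval.** This needs no new method. SAP 6.1.5 already plans "The number and percentage of participants and doses using concomitant medication (any medication, any antipyretic and any antipyretic taken prophylactically, respectively", after each vaccine dose and overall, without specifying an interval, and SAP 6.1.6 does the same for concomitant vaccinations.
- **(b) Use an effective sample size.** Apply Clopper-Pearson with n = doses / design effect. The design effect is the participant-clustered variance divided by the binomial variance, floored at 1. If no dose or every dose has the event, use n = number of participants.

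Keep Clopper-Pearson unchanged for single-dose and participant-level rows.

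The cost is that sentence and a few lines of code. Under (b), intervals widen slightly. With zero events the upper limit rises from 1 − 0.025^(1/1028) = 0.36% to 1 − 0.025^(1/514) = 0.72%. In simulation (40,000 trials per scenario, rho from 0 to 0.5 where possible), coverage under (b) was 95.2% to 95.8% at equal rates of 1%, 10%, 30% and 50%, 95.2% to 95.7% at 30% and 50%, 95.4% to 96.9% at 20% and 60%, and 98.5% to 98.7% at 0.5%. Option (b) is therefore somewhat conservative for very rare events, or when rates differ widely and rho is low. Option (a) is the simpler choice for a descriptive table. A footnote saying that within-participant correlation is ignored would be cheaper still, but it would leave the interval itself uncorrected.

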4.4. Tertiary Analyses

CCI

4.5. Safety Analyses

Safety analyses are described in Section 4.3.2.

